8.5.2 Withdrawal of Informed Consent for Donated Biological Samples

If a subject withdraws consent to the use of donated samples, the samples will be disposed of/destroyed, and the action documented. As collection of the biological samples is an integral part of the study, then the subject is withdrawn from further study participation.

The Principal Investigator:

- Ensures that biological samples from that subject, if stored at the study site, are immediately identified, disposed of /destroyed, and the action documented
- Ensures the laboratory(ies) holding the samples is/are informed about the withdrawn consent immediately and that samples are disposed/destroyed, the action documented and the signed document returned to the study site
- Ensures that the subject is informed about the sample disposal

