6.8 Treatment Discontinuation

Upon treatment discontinuation all end of treatment evaluations and tests will be conducted. All participants who discontinue due to an AE must be followed until the event resolves or stabilizes. Appropriate medical care should be provided until signs and symptoms have abated, stabilized, or until abnormal laboratory findings have returned to acceptable or pre-study limits. The final status of the AE will be reported in the participant’s medical records and the appropriate eCRF.

An individual subject will not receive any further investigational product if any of the following occur in the subject in question:

1. Withdrawal of consent or lost to follow-up.
 - a. If consent is withdrawn, the subject will not receive any further investigational product or further study observation.
2. Adverse event that, in the opinion of the investigator or the sponsor, contraindicates further dosing
3. Subject is determined to have met one or more of the exclusion criteria for study participation at study entry and continuing investigational therapy might constitute a safety risk.
4. Pregnancy or intent to become pregnant.

5. Any AE that meets criteria for discontinuation as defined in Section 10.1.
6. Adverse Event or DLT that, in the opinion of the Investigator, contraindicates further dosing (See Section 6.4 for definition of DLT).
7. Grade ≥ 3 infusion reaction.
8. Subject noncompliance that, in the opinion of the investigator or sponsor, warrants withdrawal; e.g., refusal to adhere to scheduled visits.
9. Initiation of alternative anticancer therapy including another investigational agent.
10. Confirmation of PD and investigator determination that the subject is no longer benefiting from treatment.
11. Development of intercurrent, non-cancer related illnesses that prevent either continuation of therapy or regular follow up.

Subjects who are permanently discontinued from further receipt of investigational product, regardless of the reason (withdrawal of consent, due to an AE, other), will be identified as having permanently discontinued treatment.

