Subjects who are permanently discontinued from receiving investigational product will be followed for safety per Section 10 and Appendix H or Appendix I, including the collection of any protocol-specified blood specimens, unless consent is withdrawn or the subject is lost to follow-up or started on standard therapy or enrolled in another clinical study. All subjects will be followed for survival. Subjects who decline to return to the site for evaluations will be offered follow-up by phone every 3 months as an alternative.

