8.1.5 End of Treatment

End of treatment is defined as the last planned dosing visit within the 12-month dosing period. For subjects who discontinue durvalumab or tremelimumab or olaparib prior to 12 months, end of treatment is considered the last visit where the decision is made to discontinue treatment. All required procedures may be completed within \pm 7 days of the end of treatment visit. Repeat disease assessment is not required if performed within 28 days prior to the end of treatment visit.

Follow-up assessments for subjects who have completed durvalumab, tremelimumab, and olaparib treatment and achieved disease control, or have discontinued durvalumab or tremelimumab or olaparib due to toxicity in the absence of confirmed progressive disease are provided in Appendix H.

Follow-up assessments for subjects who have discontinued durvalumab or tremelimumab treatment due to confirmed PD are presented in Appendix I.

All subjects will be followed for survival until the end of the study regardless of further treatments, or until the sponsor ends the study.

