12.4 Clinical Efficacy

Clinical efficacy evaluation will include tumor response assessed by irRECIST, Progression-free Survival and overall survival.

The primary endpoint will test the 3-month progression free survival rate in the platinum resistant group in conjunction with the 6-month progression free survival rate in the platinum sensitive group. The overall test follows the approach of London and Chang(58) Let π_1 denote the 3 month progression free response rate for the platinum-resistant strata and let π_2 denote the 6 month progression free response rate for the platinum sensitive strata. Our overall test is of the form $H_0: \pi_1 = 0.55, \pi_2 = 0.65$ versus the alternative $H_1: \pi_1 > 0.55, \pi_2 > 0.65$. Using the approach of

London and Chang our test statistic takes the form $T = \frac{R - \sum_i^2 N_i \pi_{i0}}{\sqrt{N \sum_{i=1}^2 \pi_{i0} (1 - \pi_{i0}) P_i}}$, where R denotes the combined number of non-progressors across strata, $\pi_{10} = 0.55$ and $\pi_{20} = 0.65$ represent the null values for strata 1 and 2 above, $N = N_1 + N_2$ $N_1 = 18$ and $N_2 = 9$ represent the strata sample sizes and $P_1 = 2/3$ and $P_2 = 1/3$ represent the strata distribution proportions, respectively. The distributional properties of T are given in London and Chang (58). Given $\alpha = 0.10$ and a fixed sample size of $N = 27$ we will be able to detect a difference of 0.2 and 0.15 between the null and alternative progression free survival rate values per strata one and two, respectively at 0.72 power based on an exact multinomial test about T .

All patients who received at least two cycles of durvalumab + tremelimumab and 8 weeks of olaparib, as well as baseline and at least one post-baseline disease assessment will be evaluated for clinical efficacy. Tumor Responses by irRECIST and RECIST, progression free survival and overall survival will be summarized and analyzed descriptively via summary frequencies and Kaplan-Meier estimators.

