2. INFORMED CONSENT

- Informed consent must be obtained by the **site Investigator/designee** from any participants wishing to participate, **prior to any procedures or treatment**.
- An informed consent template is provided by RPCI and can be amended to reflect institutional requirements.
- All consent changes **must** be reviewed by Roswell Park CRS QA Network Office prior to submission to the site IRB.
- The informed consent must be IRB approved.
- Always check that the most up to date version of the IRB approved consent is being used.
- Within 5 business days, notify the Roswell Park CRS QA Network Office of all participant withdrawals or consent to limited study participation and appropriately document the discontinuation and the reason(s) why.

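### Withdrawing consent to sample use alone ends all study participation (Section 8.5.2), which conflicts with survival follow-up of all subjects and discards outcome data the patient has not refused

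*Combined protocol and SAP*

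**What the plan says.** Section 8.5.2 deals with a subject who withdraws consent to the use of donated samples. The samples are destroyed, and the section adds: "As collection of the biological samples is an integral part of the study, then the subject is withdrawn from further study participation". It does not say whether scans, adverse events or vital status may still be collected.

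Four other places bear on this:

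- Section 6.8, item 1, lists withdrawal of consent among the reasons to end study drug: "If consent is withdrawn, the subject will not receive any further investigational product or further study observation". It does not separate consent to sample use from consent to the study.
- Later in Section 6.8, safety follow-up after discontinuation carries an exception for withdrawn consent. The sentence after it carries none: "All subjects will be followed for survival".
- Section 8.1.5: "All subjects will be followed for survival until the end of the study regardless of further treatments, or until the sponsor ends the study".
- Appendix A, item 2, requires network sites to "notify the Roswell Park CRS QA Network Office of all participant withdrawals or consent to limited study participation". Partial consent is therefore a recognised status.

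On the analysis, Section 12.4 states: "The primary endpoint will test the 3-month progression free survival rate in the platinum resistant group", taken together with the 6-month rate in the platinum-sensitive group. The statistic uses R, the number of non-progressors across both strata.

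**The concern.** The patient has refused one thing, the use of her samples. The samples serve the immune-response and correlative endpoints (Sections 3.2 and 13.1). The Phase II primary endpoint and overall survival need scans and vital status, which she has not refused. A site that follows Section 8.5.2 stops collecting both. A site that follows Section 8.1.5 keeps collecting survival.

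Two things are at stake. Survival follow-up can be lost at any time on study, before or after the landmark, in breach of what two other sections promise. In addition, a landmark assessment can be lost in a 27-patient test based on a count. R cannot censor a patient, so each missing landmark must be scored or excluded, and Section 12.4 does not say how to treat an evaluable patient who lacks one.

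**Working it through.** **Step 1. Who is exposed in R.** Table 5 (footnote 17) schedules scans at Cycle 4 Day 1 and every three cycles thereafter. With 28-day cycles:

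- Cycle 4 Day 1 = 1 + 3 × 28 = day 85.
- Cycle 7 Day 1 = 1 + 6 × 28 = day 169.

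The documents' own rules then sort patients by when they leave:

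- Before 8 weeks, for reasons other than DLT: replaced (Section 4.3, which says that it applies to Phase I and Phase II).
- Without any post-baseline disease assessment: outside the efficacy set (Section 12.4).
- Platinum-resistant (3-month landmark): the first scheduled scan, about day 85, is close to the landmark. A patient who leaves before it is normally replaced or excluded; one who leaves after it normally has her scan.
- Platinum-sensitive (6-month landmark): a patient who leaves between about day 85 and day 169 has a post-baseline scan, so she is in the efficacy set, but she has no assessment near 6 months. This is the main gap.

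Smaller exceptions are a patient with only an early unscheduled scan, and a resistant patient who leaves in the few days between Cycle 4 Day 1 and 3 months.

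**Step 2. Reproduce the stated power.** Inputs from Section 12.4: strata of 18 and 9, null rates 0.55 and 0.65, differences 0.20 and 0.15, α = 0.10. The test is one-sided, since H1 is above the null in both strata. The alternatives are 0.55 + 0.20 = 0.75 and 0.65 + 0.15 = 0.80.

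R = X₁ + X₂, with X₁ ~ Bin(18, p₁) and X₂ ~ Bin(9, p₂). The exact distribution comes from convolution.

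- P(R ≥ 19 | H0) = 0.140, above 0.10.
- P(R ≥ 20 | H0) = 0.068, so the cut-off is 20.
- P(R ≥ 20 | H1) = 0.717, which matches the stated 0.72.

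A normal approximation (0.778) and an exact test with random stratum sizes (0.773) do not match, so the fixed-strata exact test is used below.

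**Step 3. Lose w platinum-sensitive patients before their landmark.** The documents give no rate, so w = 1 and w = 2 are assumptions. Now X₂ ~ Bin(9 − w, p₂), with the other patients' rates unchanged.

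- Scored as progressed: P(X₁ + X₂ ≥ 20).
- Scored as progression-free: P(X₁ + X₂ ≥ 20 − w).
- Excluded: the smallest cut-off with size ≤ 0.10, which is 19 for N = 26 and 19 for N = 25.

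| Lost | Handling | Size | Power |
|---|---|---|---|
| 0 | as planned | 0.068 | 0.717 |
| 1 | progressed | 0.036 | 0.589 |
| 1 | excluded, cut-off 19 | 0.085 | 0.749 |
| 1 | progression-free | 0.085 | 0.749 |
| 2 | progressed | 0.017 | 0.442 |
| 2 | excluded, cut-off 19 | 0.047 | 0.626 |
| 2 | progression-free | 0.106 | 0.780 |

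With one patient, the choice of handling moves power by 0.749 − 0.589 = 0.160. Excluding her raises power above the plan only because the new cut-off uses more of the 0.10 (0.085 against 0.068). With two patients scored as progression-free, size passes 0.10.

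**The case against.** Section 8.5.2 states a rule and gives its reason; it is not an oversight. Anti-tumor immune response is the first-listed secondary objective (Section 3.2), and archival tissue is required of every patient (Sections 5.1 and 8.5.1.1). Section 6.8, item 1, already ends observation when consent is withdrawn, and 8.5.2 can be read as applying that to sample consent. The words on further treatments in Section 8.1.5 concern later therapy, not withdrawn consent. The consent pages are not available for review, so the form may offer levels of withdrawal.

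Much of this stands: making sampling a condition of participation is open to the sponsor. It does not remove the conflict. The survival sentences carry no exception, Appendix A recognises a status that 8.5.2 leaves no room for, and the on-treatment biopsy is taken only if clinically appropriate (Section 8.5.1.2), so patients already remain on study without it.

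Three stronger readings are tempting, and the documents do not support them:

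- *That the plan has no rule at all for such a patient.* Sections 4.3 and 12.4 deal with those who leave before 8 weeks or without a post-baseline scan.
- *That several platinum-resistant losses would erode the test.* For that stratum the first scheduled scan is nearly the landmark, so most such patients are handled by rule or already scanned.
- *That the loss would fall on sicker patients because of the sampling burden.* The trigger is withdrawal of consent to the use of samples, not a missed draw or a declined biopsy, and no section links it to health status.

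Section 6.8 also calls for end-of-treatment evaluations at discontinuation, which might recover a scan. Whether they apply once consent is withdrawn is unclear.

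**Conclusion.** The point holds as an inconsistency between sections with an avoidable loss of data, and it should be corrected. The survival conflict applies to every patient at any time on study. The effect on the primary test is confined mainly to platinum-sensitive patients who withdraw in the roughly 12 weeks between the two scans (169 − 85 = 84 days).

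For one assumed loss, power lies between 0.589 and 0.749. For two, which is 2/9 = 22% of the stratum, it lies between 0.442 and 0.780, with size up to 0.106. These figures rest on fixed strata of 18 and 9, on the plan's null and alternative rates, and on losses unrelated to outcome. The frequency is unknown and probably low, so they show what one or two such patients could do. They do not forecast a loss.

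**What to change.** Replace the sentence in Section 8.5.2 with wording to this effect: *withdrawal of consent to sample use ends research sampling and sample analysis only; unless the subject also withdraws consent to follow-up, tumor assessments, adverse event collection and survival follow-up continue under Table 5 and Appendices H and I, and her data stay in the primary, overall survival and safety analyses.*

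Reconcile Section 8.5.2 with Section 6.8 (both the consent item and the survival sentence), Section 8.1.5 and Appendix A. Those sections must also settle whether study treatment continues after a sample-only withdrawal; no answer is proposed here. Record the level of withdrawal on the eCRF.

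The new sentence prevents most of these missing landmarks but does not say how a remaining one enters R. That affects any evaluable patient without a landmark assessment, so it belongs in Section 12.4: one line naming the handling, with a sensitivity analysis under the alternatives.

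The cost is a few sentences and matching consent wording. A few patients will have no further correlative samples, but the current rule loses those too.

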9 EFFICACY EVALUATIONS

Disease Evaluation and Methods

The response to immunotherapy may differ from the typical responses observed with cytotoxic chemotherapy, including the following (50, 51):

- Response to immunotherapy may be delayed
- Response to immunotherapy may occur after PD by conventional criteria
- The appearance of new lesions may not represent PD with immunotherapy
- SD while on immunotherapy may be durable and represent clinical benefit.

Based on the above-described unique response to immunotherapy and based on guidelines from regulatory agencies, e.g., European Medicines Agency's "Guideline on the evaluation of anti-cancer medicinal products in man" (52) for immune modulating anti-cancer compounds, the study may wish to implement the following in addition to standard RECIST 1.1 criteria (53):

- RECIST will be modified so that PD must be confirmed at the next scheduled visit, preferably, and no earlier than 4 weeks after the initial assessment of PD in the absence of clinically significant deterioration. Treatment with durvalumab, tremelimumab, and olaparib would continue between the initial assessment of progression and confirmation for progression.
- In addition, subjects may continue to receive durvalumab, tremelimumab, and olaparib beyond confirmed PD in the absence of clinically significant deterioration and if investigators consider that subjects continue to receive benefit from treatment.

Modification of RECIST as described may discourage the early discontinuation of durvalumab/olaparib and provide a more complete evaluation of its anti-tumor activity than would be seen with conventional response criteria. Nonetheless, the efficacy analysis will be conducted by programmatically deriving each efficacy endpoint based on RECIST 1.1 criteria.

Of note, clinically significant deterioration is considered to be a rapid tumor progression that necessitates treatment with anti-cancer therapy other than durvalumab/olaparib or with symptomatic progression that requires urgent medical intervention (e.g., central nervous system metastasis, respiratory failure due to tumor compression, spinal cord compression).

9.1 Efficacy Assessment by irRECIST

Tumor response will be assessed using the Immune-Related Response Criteria (irRECIST) as described by Nishino et al, 2013 (54) and Bohnsack et al, 2014 (55). The Principal Investigator is responsible for ensuring that all staff involved in the study is familiar with the content of this section.

Tumor response will be assessed by irRECIST. Conventional RECIST 1.1 (53) will also be documented during the trial, however; RECIST 1.1 will not be used to determine disease progression.

Refer to Appendix K for a summary of irRECIST.

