2.3 New Non-Measurable Lesions Definition and Assessment

- All new lesions not selected as new measurable lesions are considered new non-measurable lesions and are followed qualitatively.
- Only a massive and unequivocal progression of new non-measurable lesions leads to an overall assessment of irPD for the time-point.
- Persisting new non- measurable lesions prevent irCR.

2.4 irRECIST Overall Tumor Assessments

The irRECIST overall tumor assessment is based on the **TMTB** (total measured tumor burden) of measured target and new lesions, non-target lesion assessment and new non-measurable lesions.

Time point response assessments will be performed on Cycle 4 Day 1 (± 7 days) and then every 3 cycles.

Conventional RECIST 1.1 will also be documented during the trial however; RECIST 1.1 will not be used to determine disease progression. The irRECIST will be used for tumor response assessment at time of continuing review and will be used for IRB reporting and formal analysis.

- **irCR:** Complete disappearance of all measurable and non-measurable lesions. Lymph nodes must decrease to < 10 mm in short axis. Confirmation of response is not mandatory.
- **irPR:** Decrease of $\geq 30\%$ in TMTB relative to baseline, non-target lesions are irNN, and no unequivocal progression of new non-measurable lesions.
- **irSD:** Failure to meet criteria for irCR or irPR in the absence of irPD.

- **irNN:** No target disease was identified at baseline and at follow-up the patient fails to meet criteria for irCR or irPD.
- **irPD:** Minimum 20% increase and minimum 5 mm absolute increase in TMTB compared to nadir, or irPD for non-target or new non-measurable lesions. Confirmation of progression is recommended minimum 4 weeks after the first irPD assessment.
- **irNE:** Used in exceptional cases where insufficient data exists.
- **irND:** In adjuvant setting when no disease is detected.

New Lesions: the presence of new lesion(s) does not define progression. The measurements of the new lesion(s) are included in the sum of the measurements (the sum of the measurements = the sum of the longest diameters of all target lesions and new lesions, if any).

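### The protocol gives two incompatible criteria for progression, so the event behind the primary 3- and 6-month PFS rates is undefined

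*Combined protocol and SAP*

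**What the plan says.** Section 9 describes how responses to immunotherapy can differ from those to chemotherapy, then offers a modification of RECIST under which progression has to be confirmed. That modification is optional: "the study may wish to implement the following in addition to standard RECIST 1.1 criteria". The section closes with a firm rule for the analysis: "Nonetheless, the efficacy analysis will be conducted by programmatically deriving each efficacy endpoint based on RECIST 1.1 criteria".

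Section 9.1 assesses tumor response by irRECIST, has conventional RECIST documented alongside, and states that "RECIST 1.1 will not be used to determine disease progression". Appendix K, 2.4 repeats that bar and adds: "The irRECIST will be used for tumor response assessment at time of continuing review and will be used for IRB reporting and formal analysis".

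Section 12.4 defines the test: "The primary endpoint will test the 3-month progression free survival rate in the platinum resistant group", taken together with the 6-month rate in the platinum-sensitive group. It attaches irRECIST, and later both criteria, to tumor response. PFS is listed beside tumor response with no criterion. The synopsis does the same. Neither says which criterion underlies the null rates of 0.55 and 0.65.

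**The concern.** PFS is an efficacy endpoint, and its event is progression or death. The Section 9 rule and the bar in Section 9.1 and Appendix K therefore cannot both apply to it. This goes beyond a missing detail, because the text supports two different answers.

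The protocol itself expects the two criteria to differ in some patients. Under Appendix K, "the presence of new lesion(s) does not define progression"; the measurements of new lesions are added to the tumor burden instead. Section 9 notes that "Response to immunotherapy may occur after PD by conventional criteria".

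The PFS-rate test is the only Phase II hypothesis test specified in Section 12.4. The trial is open-label and single-arm with a fixed null. If the criterion is settled after the data are seen, the nominal alpha of 0.10 no longer describes the procedure.

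There is a related gap within the irRECIST route. Appendix K says "Confirmation of progression is recommended minimum 4 weeks after the first irPD assessment", so confirmation is advised but not required. Nothing states whether unconfirmed progression counts in the analysis, or which assessment supplies its date.

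**Working it through.** **Does any other section settle the choice?**

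| Place | What it governs | Criterion |
|---|---|---|
| Section 9, closing rule | Derivation of every efficacy endpoint | RECIST 1.1 |
| Section 9.1 | Determining progression | Not RECIST 1.1 |
| Appendix K, 2.4 | Determining progression; formal analysis | Not RECIST 1.1; irRECIST |
| Section 12.4 and synopsis | Primary PFS rates | None named |
| Sections 6.2.1.2 and 6.7, Appendix H | Retreatment, treatment duration, follow-up scans | irRECIST |

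The last row concerns conduct, not analysis. Reading the plan as irRECIST for conduct and RECIST 1.1 for analysis would fit Section 9, but not Appendix K's assignment of irRECIST to formal analysis.

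**Reproducing the plan's power.** Inputs from Section 12.4: N1 = 18, N2 = 9, nulls 0.55 and 0.65, differences 0.20 and 0.15 (so alternatives 0.75 and 0.80), alpha 0.10, stated power 0.72. Let R be the number progression-free, R = Bin(18, p1) + Bin(9, p2).

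- Null mean: 18 × 0.55 + 9 × 0.65 = 15.75.
- Null variance: 18 × 0.55 × 0.45 + 9 × 0.65 × 0.35 = 6.5025, so SD = 2.55.
- T at R = 19: (19 − 15.75)/2.55 = 1.275. T at R = 20: 4.25/2.55 = 1.667.

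| Rule | Size under (0.55, 0.65) | Power under (0.75, 0.80) |
|---|---|---|
| R ≥ 19 | 0.1399 | 0.8425 |
| R ≥ 20 | 0.0682 | 0.7172 |

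The smallest cut-off with size at most 0.10 is R ≥ 20. Its power of 0.717 matches the stated 0.72, so the power figure is not in dispute. In proportions, 20/27 = 74.1% rejects and 19/27 = 70.4% does not.

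**How much probability sits at the edge?**

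- Null: P(R = 19) + P(R = 20) = 0.0717 + 0.0399 = 0.112 (unrounded sum 0.1117).
- Alternative: 0.1254 + 0.1648 = 0.290.

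At these two counts, one patient moved in the relevant direction reverses the conclusion. This is the chance of being at the edge, not the chance that the criteria disagree.

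**Illustration only.** Suppose the two criteria differ by x in the progression-free rate in both strata. The documents give no value for x.

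| Assumed x | Size: nulls fit the stricter criterion, the more lenient is used | Power: planning rates fit the more lenient criterion, the stricter is used |
|---|---|---|
| 0.03 | 0.120 | 0.581 |
| 0.05 | 0.168 | 0.487 |
| 0.10 | 0.339 | 0.275 |

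Each size is P(R ≥ 20) at rates (0.55 + x, 0.65 + x); each power is P(R ≥ 20) at (0.75 − x, 0.80 − x).

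**Dating.** Table 5, footnote 17 schedules scans at C4D1 and C7D1, ± 7 days. I assume 28-day cycles on schedule and time counted from first dose, since Section 12.4 states no origin.

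- C4D1 is day 1 + 3 × 28 = 85 (window 78 to 92). The earliest confirmation is 78 + 28 = day 106, against 3 months = 91.3 days.
- C7D1 is day 1 + 6 × 28 = 169 (window 162 to 176). The earliest confirmation is 162 + 28 = day 190, against 6 months = 182.6 days.

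If progression were dated at the confirming scan, progression first seen on these scheduled scans could not count at the landmark. No section proposes that date; none excludes it either. Unscheduled scans could fall earlier.

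**The case against.** The strongest reply is that the documents lean clearly towards irRECIST. The title of Section 9.1, the bar on RECIST 1.1, Appendix K, the opening of Section 12.4, Table 5 and the conduct sections all point that way. One sentence in Section 9 stands against them, and it follows optional text. The lean is real, but that sentence is firm, covers each endpoint, and is the only explicit rule for deriving them. The optional wording attaches to the confirmation change.

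A second reply is that Appendix K's formal-analysis sentence is about tumor response assessment, so it should not be read more broadly than the similar wording in Section 12.4. That weakens this one support, but the explicit bar on using RECIST 1.1 for progression remains.

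Third, the numbers do not measure the defect. Any exact test in 27 patients has a one-patient edge, and the assumed shifts have no source in the documents. This is fair: they show sensitivity, and the finding does not rest on them. The dating arithmetic is likewise conditional.

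Fourth, the cut-off of 20 assumes exactly 18 and 9 evaluable patients. With 17 + 9 or 18 + 8 it becomes 19 (size 0.091 or 0.085). This is correct. Section 4.3 allows replacement, so 27 may be kept, but the condition should be stated.

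Finally, Section 4.1 words the Phase II primary endpoint as a comparison with PFS on the last treatment. Section 12.4 gives no test for that comparison, so it does not resolve the conflict.

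**Conclusion.** The concern holds, and the text is wrong as written: the primary PFS rates have two incompatible progression rules, and the statistics section does not choose between them. This follows from the wording alone and needs no assumption about the data.

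The demonstrable size is that, with 18 + 9 patients, the decision turns between 19 and 20 of 27, and the result falls on one of those two counts with probability 0.112 under the null and 0.290 under the alternative. The frequency and net direction of disagreement between the criteria cannot be obtained from the documents. The stated power of 0.72 stands. Because this is the only Phase II test specified in Section 12.4, the conflict must be resolved before analysis.

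**What to change.** Before analysis, reconcile Sections 9, 9.1 and 12.4 and Appendix K, 2.4 so that one criterion defines progression for the primary PFS rates. The choice is the sponsor's. Section 12.4 should then state:

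- that criterion;
- which criterion the 0.55 and 0.65 nulls rest on, or that this is unknown;
- whether unconfirmed progression counts as an event in the analysis;
- whether the first or the confirming assessment dates progression.

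Report the PFS rates under the other criterion as a prespecified sensitivity analysis.

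The cost is text edits in four places, one additional analysis, and a check that RECIST 1.1 was recorded at each scan, since Section 9.1 asks only that it be documented during the trial. If the stricter criterion is chosen, the observed rate and the power may be lower than planned. No dose or treatment rule changes.
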